8.1.2.2.3. Sexual Frequency Questionnaire

The SFQ is a patient reported outcome measure to evaluate the impact of genital psoriasis symptoms on sexual frequency. It consists of 2 items that assess the impact of genital psoriasis symptoms on the frequency of sexual activity. Respondents are asked to answer the questions based on their psoriasis symptoms in the genital area. Genital area is defined as the labia majora (outer lip), labia minora (inner lip), and perineum (area between vagina and anus) for females; penis, scrotum, and perineum (area between the penis and anus) for males. The definition of sexual activity is not limited to intercourse and includes activities such as masturbation.

Item 1 asks how many times the patient engaged in sexual activity in the past week with response options of none/zero (2), once (1), and two or more (0).

Item 2 assesses how often genital psoriasis symptoms limited the frequency of sexual activity with response options ranging from 0 (never) to 4 (always).

The individual item scores of the SFQ are reported separately. No total score is calculated for the SFQ.

The instructions for completion are embedded within the SFQ questionnaire for patients to read before responding to the items. Prior to Week 12 (Visit 7), patients will use an e-diary, using a recall period of 1 week, and the response for each item uses a Likert scale. Thereafter, study participants will answer these questions only at scheduled study visits using the same 1-week recall period as used for the e-diary.

SFQ individual item scores at Week 12 (Visit 7) are the scores collected at Visit 7 on site.

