
 • To assess whether 80 mg ixekizumab Q2W is superior to placebo at Week 12 in the treatment of patients with moderate to severe genital psoriasis as measured by: 
 ○ GPSIS, Impact of Sexual Activity on Genital Psoriasis Symptoms Subscale for patients who reported as being sexually active at baseline (score of “0” on GPSIS Question 1) ○ Sexual Frequency Questionnaire (SFQ) item 1 ○ Comprehensive Assessment of the Psoriasis Patient (CAPP) Genital sub-index ○ Touch Avoidance NRS ○ Short Form 36 Question Health Survey (SF-36) individual domain scores 	
 • To assess whether 80 mg ixekizumab Q2W is superior to placebo at Week 12 in the treatment of patients with moderate to severe genital psoriasis as measured by: 
 ○ The proportion of patients whose degree of worsening is very low or none at all, or low, GPSIS Impact of Sexual Activity on Genital Psoriasis Symptoms Subscale score of 1 or 2, at Week 12. This will be calculated for patients who reported a score of “0” on GPSIS Question 1 at baseline and had a baseline score of at least 3 ○ The proportion of patients at each level of SFQ item 1 ○ Mean change from baseline in the total CAPP Genital sub-index score ○ Mean change from baseline in the Touch Avoidance NRS ○ The proportion of patients with at least a 5 point improvement from baseline in individual domain scores

Exploratory Objectives	Exploratory Endpoints

 To explore the impact of ixekizumab versus placebo at Week 12 on the change in presence of fissure, ulcer, and/or erosion in the genital area and its association with measures of disease severity and quality of life 	
 The proportion of patients with presence of genital fissure, ulcer, and/or erosion and the association of presence with measures of sPGA of Genitalia (0,1) response and quality of life (SF-36 mental component summary [MCS], Dermatology Life Quality Index [DLQI], GPSIS Subscales, and SFQ items) in the subgroup of patients with fissure, ulcer, and/or erosion

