5.2. Method of Assignment to Treatment

Patients who meet all criteria for enrollment will be randomized to blinded treatment at Visit 2 (Week 0) in a 1:1 ratio to ixekizumab 80 mg Q2W or placebo. Assignment to treatment groups will be determined by a computer-generated random sequence using an interactive web-response system (IWRS). The IWRS will be used to assign double-blind investigational product to each patient. Site personnel will confirm that they have located the correct assigned investigational product package by entering a confirmation number found on the package into the IWRS.

To achieve between-group comparability for body surface area (BSA), the randomization will be stratified by BSA (1% to <10% versus $\geq 10\%$).

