6.1.3. Analysis Methods

6.1.3.1. Primary Analysis Method

- **Categorical**
 - Treatment comparisons of all categorical efficacy and health outcome variables will be performed using a logistic regression model with treatment and BSA category (<10% vs ≥10% BSA at baseline) as factors, using the NRI method. The odds ratios (OR) and the corresponding 95% CIs, will be reported.
- **Continuous**
 - The primary analyses for all continuous efficacy and health outcome variables will be performed using MMRM. The model will include treatment, baseline BSA category, baseline value, visit, treatment-by-visit interaction, and baseline-by-visit interaction as fixed factors. The covariance structure to model the within-patient errors will be unstructured. If the unstructured covariance matrix results in a lack of convergence, the heterogeneous Toeplitz covariance structure, followed by the heterogeneous autoregressive covariance structure, followed by the compound symmetry will be used. The Kenward-Roger method will be used to estimate the denominator degrees of freedom. Type III tests for the least-square (LS) means will be used for the statistical comparison; the 95% CI will also be reported. Treatment group comparisons at all visits up to Week 12 will be tested. This order is specified according to a decreasing number of covariance parameters in the structure.

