SFQ	
The SFQ is a patient reported outcome measure to evaluate the impact of genital psoriasis symptoms on sexual frequency. It consists of 2 items that assess the impact of genital psoriasis symptoms on the frequency of sexual activity. Respondents are asked to answer the questions based on their psoriasis symptoms in the genital area.
 
Item 1 asks how many times the patient engaged in sexual activity in the past week with response options of: 2 = none/zero 1 = once 0 = two or more
 
Item 2 assesses how often genital psoriasis symptoms limited the frequency of sexual activity with the following response options: 0 = never 1 = rarely 2 = sometimes 3 = often 4 = always
	SFQ Item 1	
Item 1 score as reported in the weekly e-diaries. The score ranges from 0 to 2.
 
Item 1 Score at Week 12 (Visit 7) is the score collected at Visit 7 on site.
 
Item 1 Score at Week 2 (Visit 4), Week 4 (Visit 5), and Week 8 (Visit 6) is defined as the last non-missing score collected before the date of the visit, and on or after the date of previous visit.
 
Item 1 Score is the lasting non-missing score before the date of Visit 3 and on or after the date of the first injection.
 
For the visit beyond Week 12 (Visit 7), the score is as being collected at that visit on site.
	Missing if the item 1 score is missing
		SFQ Item 2	
Item 2 score as reported in the weekly e-diaries. The score ranges from 0 to 4.
 
Item 2 Score, at each post-baseline visit in the Blinded Treatment Period and Open-Label Treatment Period, is derived in the same manner as Item 1 Score.
	Missing if the item 2 score is missing

Measure	Description	Variable	Derivation	Imputation Approach if Components are Missing
	The individual item scores of the SFQ are reported separately. No total score is calculated for the SFQ.		
For exploratory analyses, Item 2 Score at each calendar week is examined, and defined as the last non-missing subscale score collected in the calendar week.
 
The calendar week is defined as follows: Calendar Week 1 is from study day 1 to 7; Calendar Week 2 is from study day 8 to 14; ... Calendar Week 11 is from study day 70 to 77; Calendar Week 12 is from study day 78 to the date of Visit 7.
 
Note that study day 1 is the date of the first injection during the Blinded Treatment Period.
	
		SFQ Item 2 Score of 0 or 1	Item 2 score is assessed as 0 or 1.	Missing if the item 2 score is missing

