	Time to at least a 3-point improvement in Itch NRS score	ITT Population: Patients with a baseline score of at least 3	During the Blinded Treatment Period	Kaplan Meier Analyses	Exploratory	Primary
SFQ ^a	Proportion of patients achieving SFQ item 2 score of 0 or 1	ITT Population: Patients with a baseline score of at least 2	Week 12 and other post-baseline visits ^b	Logistic regression analysis using NRI	Major Secondary #3 (at Week 12 only)	Primary
			Week 12 and other post-baseline visits ^b	Fisher’s exact test using NRI		Secondary
			At each calendar week ^c	Logistic regression analysis using NRI	Exploratory	Primary
			At each calendar week ^c	Fisher’s exact test using NRI		Secondary
	Proportion of patients at each level of SFQ item 1	ITT Population	Week 12 and other post-baseline visits ^b	Fisher’s exact test based on observed data	Exploratory	Primary
GPSIS ^a	Proportion of patients achieving Sexual Activity Avoidance	ITT Population: Patients with a baseline score of at least 3	Week 12 and other post-baseline visits ^b	Logistic regression analysis using NRI	Other secondary	Primary

Measure	Variable	Population (Section 6.1.1)	Time Point	Analysis and Imputation Method (Sections 6.1.3 and 6.3)	Objective/ Endpoint Type	Analysis Type
	Subscale score of 1 or 2		Week 12 and other post-baseline visits ^b	Fisher’s exact test using NRI		Secondary
			At each calendar week ^c	Logistic regression analysis using NRI	Exploratory	Primary
			At each calendar week ^c	Fisher’s exact test using NRI		Secondary
	Proportion of patients achieving Impact of Sexual Activity on Genital Psoriasis Symptoms Subscale score of 1 or 2	ITT Population: Patients with an Item 1 score of “0” and an Item 3 score of at least 3 at baseline	Week 12 and other post-baseline visits ^b	Logistic regression analysis using NRI	Exploratory	Primary
			Week 12 and other post-baseline visits ^b	Fisher’s exact test using NRI		Secondary

Measure	Variable	Population (Section 6.1.1)	Time Point	Analysis and Imputation Method (Sections 6.1.3 and 6.3)	Objective/ Endpoint Type	Analysis Type
			At each calendar week ^c	Logistic regression analysis using NRI	Exploratory	Primary
			At each calendar week ^c	Fisher's exact test using NRI		Secondary
mGPASI	Change from baseline in mGPASI	ITT Population	Week 12 and other post-baseline visits	MMRM	Other secondary	Primary
			Week 12 and other post-baseline visits	ANCOVA using mBOCF		Secondary

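### SFQ Item 1 is an ordered score with a superiority objective, but its only planned treatment comparison is an unordered Fisher test; an ordered, BSA-adjusted analysis would cost nothing

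*SAP*

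**What the plan says.** SAP Table RHBQ.6.4 describes the item: "Item 1 asks how many times the patient engaged in sexual activity in the past week with response options of" none (scored 2), once (1) and two or more (0). Protocol Section 8.1.2.2.3 gives the same scoring, so a lower score means more activity.

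The objective in SAP Section 4.3 is "To assess whether 80 mg ixekizumab Q2W is superior to placebo at Week 12", and SFQ Item 1 is one of the listed measures. The matching endpoint is "The proportion of patients at each level of SFQ item 1". It names no favourable level, score or effect measure.

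In SAP Table RHBQ.6.5 the row for "Proportion of patients at each level of SFQ item 1" has a single analysis, Fisher's "exact test based on observed data", at Week 12 and the other post-baseline visits. It is labelled exploratory, with analysis type primary.

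The SAP's general rules point elsewhere. Section 6.1.3.1 says: "Treatment comparisons of all categorical efficacy and health outcome variables will be performed using a logistic regression model", with treatment and BSA category as factors. Section 5.2 says "the randomization will be stratified by BSA", and Section 6.2 puts BSA category in Period 2 efficacy and health outcome models unless something else is specified. Footnote e of Table RHBQ.6.5 marks rows where Fisher's test replaces logistic regression as the primary method. It is not attached to this row.

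**The concern.** Whether ixekizumab is superior on a frequency item is a question about a shift towards more activity. An unordered test on three levels asks only whether the two distributions differ in some way. There are two consequences. Some power is lost for the alternative that the objective names. The test also has power for patterns that are not a shift in either direction, such as the middle level emptying equally into both ends.

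The wording leaves a second gap. One 2x3 test and three separate 2x2 tests both fit the row, and they can give different results from the same data.

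What is at stake is how one exploratory result is read. No alpha, sample size or confirmatory conclusion depends on it.

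**Working it through.** **Inputs from the documents.** Three ordered levels (Protocol 8.1.2.2.3). 73 patients per arm, two-sided 0.05 (SAP 5.3, 6.1). BSA mix of about 40:60 (SAP 6.2).

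**Assumed.** The level rates, because neither document gives any for SFQ Item 1. Three placebo distributions were tried.

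**Step 1: the plan's own figure.** SAP Section 5.3 states 94% power for 2% against 20% with Fisher's test. Full enumeration of the two-sided 2x2 Fisher test gives 94.7%, and the pooled normal formula gives 94.3%, so the figure is reproduced. It concerns DLQI Item 9. The documents state no power for SFQ Item 1.

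**Step 2: power for a consistent shift.** A common odds ratio (OR) is applied to the cumulative odds. For placebo 30/20/50% (two or more/once/none) and OR 2.0:
- two or more: odds 0.30/0.70 = 0.429; doubled, 0.857; probability 0.462
- two or more, or once: odds 0.50/0.50 = 1; doubled, 2; probability 0.667
- so ixekizumab is 46.2/20.5/33.3%

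The table shows power (%) of the 2x3 Fisher test v the ordered test (tie-corrected Wilcoxon), from 6,000 simulated trials per cell. The Monte Carlo standard error is at most sqrt(0.25/6000) = 0.65 points.

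| OR | placebo 30/20/50 | placebo 40/25/35 | placebo 20/20/60 |
|---|---|---|---|
| 1.0 (null) | 4.9 v 4.8 | 4.6 v 4.9 | 5.1 v 4.9 |
| 1.8 | 37.1 v 47.0 | 37.5 v 47.0 | 36.3 v 45.6 |
| 2.0 | 50.9 v 61.4 | 49.0 v 60.4 | 47.8 v 58.9 |
| 2.5 | 75.4 v 84.2 | 74.4 v 83.9 | 74.0 v 82.9 |
| 3.0 | 88.4 v 93.9 | 87.0 v 93.0 | 88.7 v 93.5 |

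The smallest gap is 93.5 - 88.7 = 4.8 points and the largest is 60.4 - 49.0 = 11.4 points. With 62 observed patients per arm (placebo 30/20/50, OR 2.0) the comparison is 43% v 54%.

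**Step 3: significance with no net shift.** Take counts (two or more/once/none) of 33/7/33 on ixekizumab and 25/23/25 on placebo:
- mean score, ixekizumab: (33x0 + 7x1 + 33x2)/73 = 73/73 = 1.0
- mean score, placebo: (25x0 + 23x1 + 25x2)/73 = 73/73 = 1.0
- 2x3 Fisher p = 0.005; Wilcoxon p = 1.00

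With true rates of 45/10/45% v 35/30/35%, Fisher's test is significant in about 79 to 80% of trials and the ordered test in 5%. Two other symmetric patterns gave 61% and 84% for Fisher against 5 to 6%.

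**Step 4: the per-level reading.** With three 2x2 Fisher tests and placebo 30/20/50%:
- under the null, the chance that at least one is significant is 8.6%
- at OR 2.0, the two-or-more test has 45% power and the none test 47%, against 59% for the ordered test in the same run
- under the symmetric pattern of Step 3, the once test is significant in 83% of trials

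**Step 5: what BSA stratification adds.** Strata of 29 and 44 per arm (0.4x73 and 0.6x73, rounded), placebo 30/20/50%, OR 2.0. If BSA is not prognostic: Fisher 50%, Wilcoxon 59%, stratified Wilcoxon 59%. If BSA is prognostic with an odds ratio of 2.5: 45%, 56% and 58%. Stratification adds about 0 to 2 points, so nearly all the gain comes from using the order.

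**The case against.** The strongest defence is that the test fits the endpoint as written. The endpoint is the set of level proportions, those proportions will be tabulated by arm, and a reader can see the direction beside the p-value. This stands. A reader might infer that the planned analysis cannot answer the superiority objective at all. The documents do not support that; only the p-value, taken alone, is silent on direction.

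Second, the row does not say that the test is 2x3. Per-level tests would have a direction at the two extreme levels. This also stands, but those tests are still unordered, the once level has no favourable direction, and three unadjusted tests raise the false-positive rate.

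Third, unstratified Fisher is the SAP's stated secondary method for categorical outcomes, and the table can count as the exception that Section 6.2 allows. Missing BSA adjustment is therefore a small matter, as Step 5 shows. Leaving out baseline is not peculiar to this row either, because the general logistic model has no baseline term.

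Fourth, the construct is carried by SFQ Item 2. It is Major Secondary #3, with a directional responder definition and BSA-adjusted logistic regression. The protocol's amendment summary prefers Item 2 because it does not depend on whether the patient reported, or had the chance of, sexual activity that week. Treating Item 1 mainly as description is defensible. In that case a p-value under a superiority objective is out of place.

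Finally, the no-net-shift case needs a symmetric polarisation for which there is no evident mechanism, and equal means depend on equal spacing of 0, 1 and 2. It shows what the test can do, not what to expect.

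**Conclusion.** The mismatch is real and small. An ordered score with a superiority objective has only an unordered test, in a row that departs from the general logistic-with-BSA rule without the footnote used elsewhere for that purpose. For a consistent shift the 2x3 test loses about 5 to 11 points of power against an ordered test at 73 per arm, under assumed level rates and a common odds ratio of 1.8 to 3.0. The true loss depends on rates that the documents do not give. Significance without a net shift is possible but illustrative.

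A reader might also infer a threat to the trial's conclusions. There is none: the row is exploratory and outside the sequential testing in SAP Section 6.4. This is a free improvement, not a defect that must be cured.

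**What to change.** In SAP Table RHBQ.6.5, state that lower SFQ Item 1 scores are favourable. Replace the Fisher row, at Week 12 and the other post-baseline visits in Period 2, with one ordered treatment comparison:
- a proportional odds model with treatment, BSA category and baseline Item 1 score, reporting the common odds ratio and 95% CI
- a BSA-stratified Cochran-Mantel-Haenszel row-mean-score test as the named fallback if the model does not fit
- the percentages at each level, kept as description

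SAP Section 6.1.2 already defines the baseline score. One ordered comparison also removes the ambiguity between a 2x3 test and per-level tests.

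The cost is one table row. It needs no new data and leaves the confirmatory hierarchy untouched. The one practical consequence is that a patient with no baseline Item 1 score would drop out of the model, so the number analysed should be shown.

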- d Patients who test positive for latent TB at screening, or who have a documented history of a positive TB test but do not have a documented history of at least 4 weeks of appropriate latent TB treatment, may be rescreened (Section 8.4.5). Additionally, patients who do not qualify at screening under exclusion criteria [34, 38, 39, 50] may be rescreened (1 time) as described in Section 5.3.
- e At baseline (Week 0) and Visit 7 (Week 12), BP and pulse should be measured prior to administration of the investigational product and again approximately 1 hour post-administration.
- f Habits include recording of caffeine, alcohol, and tobacco consumption.
- g Patients will record information including the date, time, and location of administration of investigational product (for treatment compliance), syringe number, who administered the investigational product, and the reason if investigational product was not fully administered in the SDAL.
- h As part of sPGA of Genitalia, the investigator will record on the eCRF (yes/no) whether psoriasis is present in women on labia minora, labia majora, and/or perineum and in men on penis (glans and/or shaft), scrotum, and/or perineum.
- i As part of mGPASI, the investigator will record on the eCRF (yes/no) if fissure, erosion, and/or ulcer are present in the genital area (defined as labia minora, labia majora, perineum for female patients and on the penis, scrotum, perineum for male patients).
- j As part of BSA, the investigator will record if psoriasis is present on the face, inframammary fold, axilla, scalp, nail, pubis, perianal region, gluteal cleft, and inguinal creases in the eCRF (yes/no) at baseline (Week 0), Week 4, 12, 24, 52, or ETV.
- k Patients should complete the scales in the following order: 1. GPSS, 2. GPSIS, and 3. SFQ. An e-diary will be used to collect these PROs up to Week 12 (V7); thereafter, patients will answer these questions only at scheduled study visits. At Week 12 (V7), patients will complete these scales on site before completion of any other assessments.
- l See Section 8.4.5 for detailed description of QuantiFERON®-TB Gold, T-SPOT®, and PPD testing.
- m A chest x-ray will be taken at screening unless one has been obtained within the past 6 months (provided the x-ray and/or report are available for review).

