6.3. Handling of Dropouts or Missing Data

The methods for imputation of missing data to be used in this study are in accordance with the precedent set in other Phase 3 psoriasis trials (Leonardi et al. 2008; Papp et al. 2008) and ixekizumab Phase 3 pivotal studies (I1F-MC-RHAZ [RHAZ], I1F-MC-RHBA [RHBA], and I1F-MC-RHBC [RHBC]).

The methods for imputation of missing data to be used in this study are described below.

6.3.1. *Non-responder Imputation (NRI)*

Analysis of categorical efficacy and health outcome variables will be based on treatment success / failure. This approach yields results numerically identical to non-responder imputation (NRI), but it is interpreted differently. Patients will be considered treatment failures if they do not meet the clinical response criteria or have missing clinical response data at a particular time point of analysis.

With NRI, as the acronym implies, there is explicit imputation of missing sPGA of Genitalia (0,1) outcomes. With treatment success / failure, discontinuation of study medication is considered a treatment failure because if patients cannot adhere to the medication they will not have sustained benefit from it. Therefore, every patient will have an observation for treatment success / failure and there will be no missing data for this estimand and hence inferences will not depend on missing data assumptions. These attributes also apply to other endpoints involving use of NRI. Randomized patients without at least 1 post-baseline observation will also be defined as non-responders for the NRI analysis.

6.3.2. *Modified Baseline Observation Carried Forward (mBOCF)*

An mBOCF analysis will be performed on the continuous efficacy and health outcome variables defined as “major” or “other” secondary outcome variables in Section 4.3. For patients discontinuing investigational product due to an adverse event (AE), including death, the baseline observation will be carried forward to the corresponding primary endpoint for evaluation. For patients discontinuing investigational product for any other reason, the last non-missing post-

baseline observation before discontinuation will be carried forward to the corresponding time point of evaluation. Randomized patients without at least 1 post-baseline observation will not be included for evaluation with the exception of patients discontinuing study treatment due to an AE (including death).

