Psoriasis on inframammary fold	Proportion of patients with absence of psoriasis on inframammary fold	ITT Population – Patients with presence of psoriasis on inframammary fold at baseline	Week 12 and other post-baseline visits	Fisher’s exact test using NRI	Exploratory	Primary ^e
sPGA of Genitalia and genital fissure/erosion/ulcer	Proportions of patients with absence of genital fissure, compared between two groups of patients achieving and not achieving sPGA of Genitalia (0,1) ^d	ITT Population – Patients with genital fissure at baseline	Week 12	Fisher’s exact test using NRI	Exploratory	Primary ^e
	Proportions of patients with absence of genital erosion, compared between two groups of patients achieving and not achieving sPGA of Genitalia (0,1) ^d	ITT Population – Patients with genital erosion at baseline	Week 12	Fisher’s exact test using NRI	Exploratory	Primary ^e
	Proportions of patients with absence of genital fissure/erosion/ulcer, compared between two groups of patients achieving and not achieving sPGA of Genitalia (0,1) ^d	ITT Population – Patients with genital fissure, erosion, and/or ulcer at baseline	Week 12	Fisher’s exact test using NRI	Exploratory	Primary ^e

Measure	Variable	Population (Section 6.1.1)	Time Point	Analysis and Imputation Method (Sections 6.1.3 and 6.3)	Objective/ Endpoint Type	Analysis Type
SFQ Item 1 and genital fissure/ erosion/ ulcer	Proportion of patients with SFQ Item 1 score response level, compared between two groups of patients with presence/absence of genital fissure ^d	Intent to Treat Population – Patients with genital fissure at baseline	Week 12	Fisher’s exact test	Exploratory	Primary ^e
	Proportion of patients with SFQ Item 1 score response level, compared between two groups of patients with presence/absence of genital erosion ^d	Intent to Treat Population – Patients with genital erosion at baseline	Week 12	Fisher’s exact test	Exploratory	Primary ^e
	Proportion of patients with SFQ Item 1 score response level, compared between two groups of patients with presence/absence of genital fissure, erosion, and /or ulcer ^d	Intent to Treat Population – Patients with genital fissure, erosion, and/or ulcer at baseline	Week 12	Fisher’s exact test	Exploratory	Primary ^e

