SF-36 MCS and facial psoriasis	Proportion of patients with SF-36 MCS ≥ 2.5 improvement, compared between two groups of patients with presence/absence of facial psoriasis ^d	Intent to Treat Population – Patients with facial psoriasis at baseline	Week 12	Fisher’s exact test using NRI	Exploratory	Primary ^e

- a Patients should complete the scales in the following order: 1. GPSS, 2. GPSIS, and 3. SFQ. An e-diary will be used to collect GPSS daily, GPSIS and SFQ weekly, up to Week 12 (Visit 7); thereafter, patients will answer these questions only at scheduled study visits. At Week 12 (Visit 7), patients will complete these scales on site before completion of any other assessments.
- b The scores at each post-baseline visit for GPSS, GPSIS and SFQ, in the Blinded Treatment Period and Open-Label Treatment Period, are defined in Table.RHBQ.6.4.
- c The scores at each calendar week in the Blinded Treatment Period, for GPSS, GPSIS and SFQ, are defined in Table.RHBQ.6.4.
- d The variables are derived based on all patients in the analysis population, not for placebo or ixekizumab treated patients separately.
- e The Primary Method for this analysis is the Fisher's exact test instead of the logistic regression model.

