6.11. Analysis Methodology for Primary and Major Secondary Outcomes

The primary endpoint for this study is the proportion of patients achieving treatment success, defined as achieving sPGA of Genitalia (0,1) at Week 12 (end of the Blinded Treatment Period) and remaining on the initially randomized treatment (i.e. the effect attributable to the originally randomized treatment, ixekizumab Q2W). With this estimand any patient who discontinues treatment prior to Week 12 is considered a treatment failure through the use of the NRI. The numeric result for treatment success/failure is identical to NRI but interpreted differently and has different consequences for missing data. With NRI, as the acronym implies, there is explicit imputation of missing sPGA of Genitalia (0,1) outcomes. With treatment success/failure, discontinuation of study medication is considered a treatment failure because if patients cannot adhere to the medication they will not have sustained benefit from it. Therefore, every patient will have an observation for treatment success/failure and placebo, at the primary time point of Week 12 in all randomized patients) and there will be no missing data for this estimand and hence inferences will not depend on missing data assumptions. These attributes also apply to other endpoints involving use of NRI.

The major secondary endpoints for this study are

1. The proportion of patients achieving an overall sPGA (0,1) at Week 12.
2. The proportion of patients with at least a 3 point improvement in genital psoriasis itch NRS within the GPSS at Week 12. This will be calculated for patients who had baseline score of at least 3.
3. The proportion of patients achieved a SFQ Item #2 score of 0 or 1 at Week 12. This will be calculated for patients who had baseline score of at least 2.

The primary analysis method for the primary endpoint will be based on a logistic regression analysis with treatment and BSA category as factors in the model and compare the ixekizumab Q2W dosing versus placebo at Week 12 (Visit 7) using the ITT Population (Section 6.1.3).

The primary analysis method for the major secondary endpoint #1-3 will be based on a logistic regression analysis with treatment and BSA category as factors in the model and compare the ixekizumab Q2W dosing versus placebo at Week 12 (Visit 7) using the ITT population (Section 6.1.3).

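### In the three exploratory rows testing genital lesion clearance against sPGA of Genitalia (0,1), NRI codes a patient with no Week 12 visit as failing both variables, which biases the association upward

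*SAP*

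**What the plan says.** In SAP Section 6.10, Table RHBQ.6.5, the block on sPGA of Genitalia and genital fissure/erosion/ulcer has three rows. The first is "Proportions of patients with absence of genital fissure, compared between two groups of patients achieving and not achieving sPGA of Genitalia (0,1", in the ITT subset described as "Patients with genital fissure at baseline". The other two replace fissure with erosion, and with any of fissure, erosion or ulcer. All three are at Week 12, use Fisher's exact test with NRI, and are labelled exploratory. Footnote d pools the arms: "The variables are derived based on all patients in the analysis population, not for placebo or ixekizumab treated patients separately".

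SAP Section 6.3.1 sets the NRI rule: "Patients will be considered treatment failures if they do not meet the clinical response criteria or have missing clinical response data" at the time point analysed. SAP Section 6.11 applies it to the grouping variable: "any patient who discontinues treatment prior to Week 12 is considered a treatment failure through the use of the NRI". It then widens the scope: "These attributes also apply to other endpoints involving use of NRI".

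The protocol's Schedule of Activities (Appendix 2) has sPGA of Genitalia and mGPASI at the same visits. Lesion status belongs to the latter: "As part of mGPASI, the investigator will record on the eCRF (yes/no) if fissure, erosion, and/or ulcer are present in the genital area". A missed Week 12 visit therefore loses both variables.

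Nothing in these rows exempts the grouping variable from NRI, removes patients with no Week 12 data, or adds an observed-data check.

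**The concern.** NRI is a familiar and usually cautious device when one outcome is compared between randomised arms. Here the two variables being related are both outcomes, and the same missing visit sets both to failure. Every such patient is a non-responder with a lesion not cleared, so the table gains concordant pairs that carry no information about whether clearing of fissures or erosions goes with a better sPGA. SAP Section 4.3 states the objective as the association of lesion presence with sPGA response and quality of life. Part of the reported association could simply be dropout. This is separate from the pooling of arms: it would arise within one arm and with no treatment effect.

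**Working it through.** **Plan's own figure.** The SAP gives no number for these rows. Its only Fisher-based figure is the sample size in Section 5.3: 73 per group, 2% versus 20%, two-sided 0.05, 94% power. Exact enumeration of the two binomials gives 94.7%, so the figure reproduces.

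**Inputs.** From the documents: the test, two-sided testing (SAP Section 6.1), the NRI rule, the shared visit and the pooling. Assumed, because the documents do not give them: p, the proportion achieving sPGA (0,1) among patients seen; q, the proportion with the lesion absent among patients seen; d, the fraction with no Week 12 visit, unrelated to either variable; and n, the size of the lesion subgroup.

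**Odds ratio.** With independence among patients seen, the expected cell proportions are:

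- achieved, absent: (1−d)pq
- achieved, not absent: (1−d)p(1−q)
- not achieved, absent: (1−d)(1−p)q
- not achieved, not absent: (1−d)(1−p)(1−q) + d

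The cross-product ratio is OR = 1 + d/[(1−d)(1−p)(1−q)], which exceeds 1 for every d > 0. Independence is needed only to make the true value 1. In any table, adding patients to the fail/fail cell alone raises the odds ratio above that of the observed pairs.

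**Illustration.** With 100 patients, d = 10% and p = q = 50%, the 90 seen split 22.5 per cell and 10 join the last cell. Lesion absence is 22.5/45 = 50% in responders and 22.5/55 = 41% in non-responders. OR = (22.5 × 32.5)/(22.5 × 22.5) = 1.44.

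**At d = 10%.** Rejection is by exact enumeration of the Fisher test at two-sided 0.05.

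| p / q | OR | Rejection, n = 40 | Rejection, n = 120 |
|---|---|---|---|
| 40% / 40% | 1 + 0.1/0.324 = 1.31 | 5% | 9% |
| 50% / 50% | 1 + 0.1/0.225 = 1.44 | 5% | 15% |
| 40% / 70% | 1 + 0.1/0.162 = 1.62 | 7% | 19% |
| 70% / 70% | 1 + 0.1/0.081 = 2.23 | 17% | 50% |

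With nothing missing, the same settings reject in about 3% to 4% of tables.

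**Where it stays below 5%.** At 50/50 and n = 30, rejection is 3.0% with 5% missing and 4.3% with 10%. Over assumed pairs from 30/50 to 70/80, rejection first passes 5% at a missing fraction of 2.7% to 14.8% for n = 30, 1.7% to 8.8% for n = 60, and 1.1% to 5.6% for n = 100.

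**Observed pairs only.** Under the same null, OR = 1.00 and rejection is 1.8% to 3.9% for n = 30 to 100 and d = 5% to 20%.

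**Pooling.** Suppose sPGA response is 60% versus 10% and lesion absence 80% versus 50% by arm, with independence within each arm and nothing missing. The pooled cells are 0.265, 0.085, 0.385 and 0.265. OR = (0.265 × 0.265)/(0.085 × 0.385) = 2.15, with 19% rejection at n = 60. Dropping NRI without stratifying would leave this second artefact in place.

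**The case against.** The best defence is the SAP's own estimand. Sections 6.3.1 and 6.11 treat discontinuation as failure by definition, so on that reading the fail/fail code is a defined outcome and nothing is imputed. This is coherent for comparing arms. For these rows it means that part of the association is discontinuation agreeing with itself, which does not answer the Section 4.3 objective.

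Two further points stand. The rows are exploratory and outside the Section 6.4 sequence. Exact independence of lesion clearing and genital severity is also hardly a credible null, so overstated strength matters more than a false-positive rate.

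A reader might infer that type I error is inflated whatever the data. The documents do not support that: Fisher's test is conservative, and with a small subgroup and few missing visits it can stay under 5%. The 70/70 row in particular is a stress case, since a pooled response of 70% would need something like 80% and 60% in the two arms. A reader might also infer that the SFQ Item 2, GPSIS, DLQI and SF-36 rows share the fault. There lesion status is the grouping variable, and Section 6.3.1 does not say that a grouping variable is imputed. Those rows are ambiguous, not shown to be wrong.

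**Conclusion.** The point holds for the three sPGA-by-lesion rows. The direction is certain: coding missed visits as failure on both variables raises the odds ratio above that of the observed pairs. The size rests on assumed rates, dropout and subgroup size, and on missingness unrelated to both variables. At 10% missing it is an odds ratio of 1.31 to 2.23 where the truth is 1. Whether the Fisher test exceeds 5% depends on those same unknowns. The consequence is minor: an overstated exploratory association, with no bearing on the primary or major secondary tests.

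**What to change.** In the three rows, replace NRI with an analysis of patients who have both variables observed at Week 12, and report the number excluded by arm. Because footnote d pools the arms, stratify by treatment, for example with an exact Cochran-Mantel-Haenszel test. The NRI version can be kept as a sensitivity analysis. For the other association rows that name NRI, add a sentence saying that lesion status, as the grouping variable, is not imputed. The table already has a precedent: SFQ Item 1 by treatment is tested on observed data, and the SFQ Item 1 association rows do not name NRI.

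The cost is a change of table wording and a slightly smaller n. Complete pairs also carry an assumption, that missingness does not depend jointly on the two variables; if it does, they can distort the association too. The exclusion counts and the retained NRI version help a reader judge that.
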